cfDNA = cell-free deoxyribonucleic acid; Cx = Cycle x; ECG = electrocardiogram; ECOG = Eastern Cooperative Oncology Group; EOT = end of treatment; PD = progressive disease; Q3M = every 3 months; Q3W = every 3 weeks; Q4W = every 4 weeks; Q6W = every 6 weeks; Q12W = every 12 weeks.

^a Screening evaluations are to be conducted within 28 days of the first dose of protocol therapy. Some screening procedures may occur on Cycle 1 Day 1 as appropriate. Informed consent must be obtained prior to any study-specific procedures and may be obtained prior to the 28-day screening window.

^b Ninety (90) days after the last dose there is a visit with assessments *if no alternative therapy has started*. If the participant has started alternative therapy within that 90 days after the last dose, the first follow up visit will be contact by telephone only.

^c For a maximum of 2 years from the last dose, participants will be contacted by telephone every 3 months to determine their survival status.

^d Cancer history will include stage, date of diagnoses, and prior cancer therapies and procedures.

^e Pregnancy tests (serum or urine) will be performed at Screening (within 24 hours of first dose), on Day 1 of every cycle thereafter (within 24 hours of dose), and EOT.

^f Pulse oximetry will be collected with vital signs only at baseline.

^g Tumor markers, (eg, CA19-9, PSA, etc) will be collected if performed as part of standard of care.

^h cfDNA (blood) will be assessed at Screening, preinfusion Cycle 2 Day 1, and EOT.

ⁱ Circulating soluble analytes and blood immune biomarkers will be assessed at Screening, preinfusion Cycle 1 Days 1 and 8, Cycles 2-4 Day 1, and EOT.

^j Stool collection will be assessed at Screening and at Cycle 2 Day 1, if possible. If this timing is not possible, any stool sample collected while on treatment would be acceptable.

^k Participants will undergo 3 tumor biopsies: mandatory baseline biopsy (for treatment assignment based on percent of tumoral CD8 cells), as early as possible after the 2nd dose of nivolumab (Day 2 – Day 10 of Cycle 2; however, any on treatment biopsy after Day 1 of Cycle 2 will be accepted, if medically feasible), and at PD (if medically feasible) prior to the optional addition of ipilimumab. Regardless of dosing, participants should continue to follow assessments as timed.

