^l If the results of the baseline screening biopsy are not adequate to obtain information on the percentage of tumoral CD8 cells for treatment assignment, a 2nd baseline biopsy may be obtained, if it is medically feasible and the participant is willing to undergo another tumor biopsy. Additionally, if the results of the on treatment biopsy are not adequate to obtain information on the percentage of tumoral CD8 cells, a 2nd on treatment biopsy may be obtained, if it is medically feasible and the participant is willing to undergo another tumor biopsy.

^m All AEs, SAEs, and all concomitant medications will be collected from the time the participant signs informed consent until 100 days after the last dose of study intervention. Prior to initiation of study intervention, only AEs and SAEs that are related to a protocol mandated intervention, including those that occur prior to assignment of study procedures (eg, screening invasive procedures, such as biopsies) should be reported. Trial-limiting toxicities can be found in [Section 8.3.7](#).

- ⁿ Nivolumab monotherapy will be administered at 360 mg IV Q3W for 4 cycles. Participants who continue to show clinical benefit after the first disease assessment will receive nivolumab at 480 mg IV Q4W until PD or intolerable toxicity (starting at Cycle 5).
- ^o Beginning at Cycle 5, nivolumab maintenance (nivolumab at 480 mg IV Q4W) will be administered until PD or intolerable toxicity.
- ^p Scans will be performed within 7 days prior to Day 1 of Cycle 4, Cycle 6, and every *even* cycle thereafter until death, disease progression, initiation of another systemic anticancer therapy, loss to follow-up, withdrawal of consent, or study termination, whichever occurs first (See [Section 8.1](#)). In addition, ad hoc scans, as part of standard of care, will be collected for participants who have discontinued treatment for reasons other than radiographic progression and prior to any alternate therapies.

Table 2: Schedule of Assessments Advanced Metastatic Cancer (Nivolumab and Ipilimumab Arm: Nivolumab Q3W and Ipilimumab Q3W [Doses 1 & 2], then Q6W [Doses 3 & 4], Followed by Single-agent Nivolumab Q4W)

Tests & Procedures	Screening ^a	On-Treatment Evaluations											End of Treatment	Follow-up	
		C1		C2	C3	C4	C5	C6	C7	C8	C9	C10		15-30 days after last dose	First visit (90 days after last dose) ^b
Day	0	D1	D8	D1	D1	D1	D1	D1	D1	D1	D1	D1	15-30 days after last dose	First visit (90 days after last dose) ^b	Q3M for 2 years ^c

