Window (days)	-28 to 0	--	± 3	± 3	± 3	± 3	± 3	± 3	± 3	± 3	± 3	± 3	± 7	± 7	± 7
Informed consent ^a	X														
Medical, cancer history ^d	X														
Physical examination	X			X	X	X	X	X	X	X	X	X	X	X	
Pregnancy test (serum or urine) ^e	X ^e			X	X	X	X	X	X	X	X	X	X		
ECOG performance status	X			X	X	X	X	X	X	X	X	X	X	X	
Vital signs (see Section 8.2.3) ^f	X	X		X	X	X	X	X	X	X	X	X	X	X	
Body weight	X	X		X	X	X	X	X	X	X	X	X			
Hematology (see Table 10)	X		X	X	X	X	X	X	X	X	X	X	X	X	
Clinical chemistry (see Table 10)	X		X	X	X	X	X	X	X	X	X	X	X	X	
Urinalysis	X		X	X	X	X	X	X	X	X	X	X	X	X	
12-lead ECG	X														
Tumor markers ^g	X			X	X	X	X	X	X	X	X	X	X		
cfDNA (blood) ^h	X			X									X		
Circulating soluble analytes ⁱ	X	X	X	X	X	X							X		
Blood immune biomarkers ⁱ	X	X	X	X	X	X							X		
Stool collection ^j	X			X											
Tumor biopsy ^k	X ^l	As early as possible after the 2nd dose ^k of ipilimumab and after the 4th dose of ipilimumab													
Concomitant medications ^m	X	X	X	X	X	X	X	X	X	X	X	X	X	X	X
Adverse events ^m	X	X	X	X	X	X	X	X	X	X	X	X	X	X	X
Nivolumab administration ⁿ		X		X	X	X	X	X	X ^o	X	X	X			
Ipilimumab administration ⁿ		X		X		X		X							

Tests & Procedures	Screening ^a	On-Treatment Evaluations											End of Treatment	Follow-up	
		C1	C2	C3	C4	C5	C6	C7	C8	C9	C10				
Day	0	D1	D8	D1	D1	D1	D1	D1	D1	D1	D1	D1	15-30 days after last dose	First visit (90 days after last dose) ^b	Q3M for 2 years ^c
Window (days)	-28 to 0	--	± 3	± 3	± 3	± 3	± 3	± 3	± 3	± 3	± 3	± 3	± 7	± 7	± 7
Follow-up for overall survival ^c														X	X
Assess subsequent cancer therapy													X	X	X
Disease assessment ^p	X	Cycle 4 Day 1, then beginning at Cycle 6 Day 1, repeat every 8 weeks (± 7 days) until radiographic progression or the start of subsequent therapy, whichever comes first													

cfDNA = cell-free deoxyribonucleic acid; Cx = Cycle x; ECG = electrocardiogram; ECOG = Eastern Cooperative Oncology Group; Q3M = every 3 months; Q3W = every 3 weeks; Q4W = every 4 weeks; Q6W = every 6 weeks; Q12W = every 12 weeks.

^a Screening evaluations are to be conducted within 28 days of the first dose of protocol therapy. Some screening procedures may occur on Cycle 1 Day 1 as appropriate. Informed consent must be obtained prior to any study-specific procedures and may be obtained prior to the 28-day screening window.

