8.3 ADVERSE EVENTS AND SERIOUS ADVERSE EVENTS

The definitions of an AE or SAE can be found in [Appendix 5](#).

Investigators will seek information on AE at each participant contact. AEs reported by the participant (or, when appropriate, by a caregiver, surrogate, or the participant's legally authorized representative) or noted by study personnel will be recorded in the participant's medical record and on the Adverse Event eCRF page.

The Investigator and any qualified designees are responsible for detecting, documenting, and recording events that meet the definition of an AE or SAE and remain responsible for following up AEs that are serious, considered related to the study intervention or study procedures, or that caused the participant to discontinue the study intervention (see [Appendix 5](#)).

8.3.1 Time Period and Frequency for Collecting AE, SAE, and Other Reportable Safety Event Information

All AEs and SAEs will be collected from the time the participant signs informed consent until 100 days after the last dose of study intervention.

Prior to initiation of study intervention, only AEs and SAEs that are related to a protocol-mandated intervention, including those that occur prior to assignment of study procedures (eg, screening invasive procedures, such as biopsies) should be reported. After obtaining informed consent, but prior to initiation of study intervention, other medical occurrences will be recorded as medical history.

If the Investigator learns of any SAE, including a death, at any time after the end of the AE reporting period, and he/she considers the event to be reasonably related to the study intervention or study participation, the Investigator must promptly notify the Sponsor or its designee. The Investigator should report these events directly to the Sponsor or its designee, either by faxing or emailing the Serious Adverse Event Report Form (SAE Report Form).

The method of recording and reporting of AE and SAE are provided in [Appendix 5](#). The procedure for submitting SAE reports is provided in [Section 8.3.8.2](#).

The method of reporting all deaths are provided in [Appendix 5](#).

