### 5.6.2 Adverse Events

All reported AEs will be coded using a recent version of the Medical Dictionary for Regulatory Activities (MedDRA) and graded using the NCI Common Terminology Criteria for Adverse Events (CTCAE) version 5.0.

A treatment-emergent adverse event (TEAE) is defined as any event that either occurs after the initiation of study intervention, having been absent at baseline, or, if present at baseline, appears to have worsened in severity or frequency, whether or not the event is considered related to study intervention. A treatment-related adverse event (TRAE) is defined as any TEAE assessed by the Investigator to be ‘Possibly’, ‘Probably’, or ‘Definitely’ related to any study intervention, as well as AEs with missing relationship. An immune-related adverse event (IRAE) is defined as a TRAE that matches a select list of coded preferred terms that have been identified by medical review.

Handling of missing and partial-missing AE dates is described in Section 5.8.1.

The incidence of AEs will be summarized by study intervention group for the following categories:

- All TEAEs
- All TRAEs
- Grade 3-4 TEAEs and TRAEs
- Serious adverse events (SAEs)
- Deaths due to an AE
- AEs leading to treatment discontinuation
- All irAEs

Treatment-emergent and treatment-related AEs will also be summarized by coded preferred Term, system organ class, and severity. In addition, separate summaries will be generated for SAEs.

The following listings will be generated:

- TEAEs
- SAEs
- AEs leading to treatment discontinuation
- Deaths, including primary cause of death

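### AE collection runs to Day 100 but the nearest visit is Day 90 ± 7, Table 2 alone marks AEs at the 3-monthly calls, and the SAP's open-ended TEAE window does not correct for either

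*Protocol*

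**What the plan says.** **Collection period.** Footnote m in Tables 1 and 2 and footnote l in Tables 3 and 4 (Protocol 1.3) state that AEs, SAEs and concomitant medications "will be collected from the time the participant signs informed consent until 100 days after the last dose of study intervention". Section 8.3.1 sets the same limit for AEs and SAEs in every arm: "until 100 days after the last dose of study intervention".

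**Contacts after treatment.** Footnote b of each table reads "Ninety (90) days after the last dose there is a visit with assessments", provided no alternative therapy has started; otherwise that contact is by telephone. The column window is ± 7 days. After it, under footnote c, "participants will be contacted by telephone every 3 months to determine their survival status", for at most 2 years from the last dose. Section 8.3 separately tells investigators to ask about AEs whenever they have contact with a participant.

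**Grid marks.** The AE and concomitant medication rows are marked at the 90-day visit in all four tables. Only Table 2 also marks them in the 3-monthly column, and its AE row, "Adverse events ^m", carries the 100-day footnote.

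**Analysis.** SAP 5.6.2 says: "A treatment-emergent adverse event (TEAE) is defined as any event that either occurs after the initiation of study intervention" and was absent at baseline, or worsened from baseline. It gives no last day. The protocol's definition (Appendix 5, 10.5.1.4) gives none either. AE incidence is summarized by study intervention group.

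**The concern.** A collection period needs a contact at or after its end. Here the only nearby visit closes before Day 100, so events at the end of the period are left to a call roughly three months later. The interval is not an idle one: Protocol 6.6.1.1 says immune-related events may appear several months after the last dose.

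The second difficulty is that one arm's grid asks for AEs long after collection is meant to have stopped. Section 8 of the protocol requires the scheduled activities to be performed and documented. A Table 2 site that records new AEs at the 3-monthly calls can say it is following the protocol, and so can a Table 1 site that does not. The SAP, which supersedes the protocol where they differ, has no cut-off to remove the extra entries. They could include events that arise on subsequent therapy. An entry with a missing relationship would also count as treatment-related under SAP 5.6.2.

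What is at stake is the secondary safety endpoint, AE incidence and severity. Even purely descriptive tables by group need one observation window if they are to be read side by side.

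**Working it through.** **1. Which columns are marked.** The number of marks in each AE row was set against the number of cells in the same table's window row.

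| Schedule | Arm | Columns | AE marks | 3-monthly column |
|---|---|---|---|---|
| Table 1 | Metastatic, nivolumab | 13 | 12 | blank |
| Table 2 | Metastatic, combination | 15 | 15 | marked |
| Table 3 | Prostate, nivolumab | 8 | 7 | blank |
| Table 4 | Prostate, combination | 10 | 9 | blank |

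The concomitant medication rows follow the same pattern. A slip in reading the PDF is unlikely. In Table 2 the overall-survival row fills the last two columns and the physical-examination row stops one column short, so the fifteenth cell is the 3-monthly column.

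**2. Days between the visit and the end of collection.** Inputs are the visit at Day 90 ± 7 (footnote b and the window row) and the limit at Day 100 (footnotes m and l, Section 8.3.1). Gap = 100 − visit day.

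- Visit on Day 97: 100 − 97 = 3 days
- Visit on Day 90: 100 − 90 = 10 days
- Visit on Day 83: 100 − 83 = 17 days

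Days 98 to 100 lie after the visit window in every case.

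**3. The next scheduled call.** Assume 3 months is 91 days, counted from the nominal visit. Then 90 + 91 = Day 181, and ± 7 gives Day 174 to Day 188. An event on Days 91 to 100 would be recalled 181 − 100 = 81 to 181 − 91 = 90 days later at the nominal call.

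**4. Extra AE marks in Table 2.** Two years of quarterly contacts is 24 / 3 = 8. The first is the 90-day visit, which every table marks, so Table 2 has about 8 − 1 = 7 AE contacts that the other grids lack.

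**5. What the texts do to an event after Day 100.**

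- Under footnote m or l and Section 8.3.1, it is not collected in any arm. The exception is an SAE judged reasonably related, which stays reportable in all arms.
- Under the grids, it is asked about at about 7 calls in the Table 2 arm and at none in the others.
- Under SAP 5.6.2, once it is in the database it counts, because nothing excludes it by date.

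The first two instructions conflict, and the third does not settle the conflict.

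**The case against.** The case against has real force.

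- **Day 90 is not the last AE contact.** Section 8.3 has AEs sought at each contact, and the 3-monthly calls are contacts in every arm. Footnote c gives their purpose but does not restrict them to survival; Table 1 itself schedules subsequent cancer therapy there. Events on Days 91 to 100 can be picked up late. This stands, and a reader who infers that they are simply lost goes too far. What remains is dating and grading an event by telephone after 81 to 90 days.
- **The 100-day limit is the same everywhere.** Table 2's AE row carries footnote m. If the footnote is obeyed, no unequal counting arises. This also stands, and it is why the point is a risk.
- **The Table 2 marks could mean follow-up of ongoing AEs** under Section 8.3.2. That is possible, but Section 8.3.2 applies to all arms, and the other three tables leave the cell blank.
- **Other contacts exist.** Participants who stop for reasons other than progression continue tumor assessments, and prostate participants may use the symptom app up to Day 100. Neither covers everyone, and Section 8.8 keeps app data out of the study database.
- **Little formally depends on it.** SAP 5.4 disclaims comparisons between groups. Trial-limiting toxicity uses the initial 12 weeks, and the prostate cohort decision uses the first cycle. This stands and limits the consequence to the descriptive safety tables.

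A reader might also infer that the combination's apparent excess toxicity would be partly an artifact of longer questioning. The documents do not support that. It requires sites to set aside both the footnote and Section 8.3.1, and it cannot describe the prostate combination arm, whose grid matches the nivolumab grids.

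**Conclusion.** The AE schedule is internally inconsistent in two places. Collection runs to Day 100, but the nearest scheduled visit falls 3 to 17 days before it (nominally 10), with the following call at about Day 181. Table 2 alone also marks AEs and concomitant medications at about 7 later calls, contrary to its own footnote and to Tables 1, 3 and 4. With no end date in the SAP's TEAE definition, late entries from Table 2 sites would be counted for the metastatic combination arm only.

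The day counts follow from the documents; the call date assumes a 91-day quarter. The effect on AE incidence cannot be computed. It needs the rate of new AEs after Day 100, the share of sites following the grid, and the length of follow-up, and the documents give none of the three as a usable figure. SAP 3.4 requires only 9 months of follow-up for the study report, so 2 years of calls need not be in that analysis. If incidence is counted per participant, a late event changes a category only for someone with no earlier event in it. Any percentage attached to this point would therefore rest on assumed rates.

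The correction is still worth making, because it is cheap and gives every group the same window.

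**What to change.** 1. In SAP 5.6.2, end the TEAE window at last dose + 100 days for all groups. This alone removes unequal counting, including from data already collected.
2. Reconcile the AE and concomitant medication marks in Table 2's 3-monthly column with footnote m and with Tables 1, 3 and 4. Related SAEs learned of later stay reportable under Section 8.3.1.
3. In Tables 1 to 4, keep the Day 90 visit with its examination and laboratory tests, and add a telephone contact for AEs and concomitant medications at Day 100 (+7) after the last dose.

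The cost is one short call per participant, edits to the schedule tables and one sentence in the SAP. Because the Day 90 visit does not move, no safety laboratory test or examination is delayed.

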^m All AEs, SAEs, and all concomitant medications will be collected from the time the participant signs informed consent until 100 days after the last dose of study intervention. Prior to initiation of study intervention, only AEs and SAEs that are related to a protocol mandated intervention, including those that occur prior to assignment of study procedures (eg, screening invasive procedures, such as biopsies) should be reported. Trial-limiting toxicities can be found in [Section 8.3.7](#).

- ⁿ Nivolumab monotherapy will be administered at 360 mg IV Q3W for 4 cycles. Participants who continue to show clinical benefit after the first disease assessment will receive nivolumab at 480 mg IV Q4W until PD or intolerable toxicity (starting at Cycle 5).
- ^o Beginning at Cycle 7, nivolumab maintenance (nivolumab at 480 mg IV Q4W) will be administered until PD or intolerable toxicity.
- ^p Scans will be performed within 7 days prior to Day 1 of Cycle 4, Cycle 6, and every *even* cycle thereafter until death, disease progression, initiation of another systemic anticancer therapy, loss to follow-up, withdrawal of consent, or study termination, whichever occurs first (See [Section 8.1](#)). In addition, ad hoc scans, as part of standard of care, will be collected for participants who have discontinued treatment for reasons other than radiographic progression and prior to any alternate therapies.

Table 3: Schedule of Assessments Advanced Prostate Cancer (Nivolumab Only Arm: Nivolumab 360 mg Q3W and Maintenance 480 mg Q4W)

Tests & Procedures	Screening ^a	On-Treatment Evaluations				End of Treatment	Follow up ^b	
		C1		C2-4	C5 Onwards		15-30 days after last dose	First visit (90 days after last dose) ^b
Day	0	D1	D8	D1	D1			
Window (days)	-28 to 0	--	± 3	± 3	± 3	± 7	± 7	± 7
Informed consent ^a	X							
Medical, cancer history ^d	X							
Physical examination	X			X	X	X	X	
ECOG performance status	X			X	X	X	X	
Vital signs (see Section 8.2.3) ^e	X	X		X	X	X	X	
Body weight	X	X		X	X			
Hematology (see Table 10)	X		X	X	X	X	X	
Clinical chemistry (see Table 10)	X		X	X	X	X	X	
Urinalysis	X		X	X	X	X	X	
12-lead ECG	X							
PSA ^f	X	X	PSA will be collected every cycle throughout treatment			X		
ctDNA (blood) ^g	X			X ^g		X		
Circulating soluble analytes ^h	X	X	X	X		X		
Blood immune biomarkers ^h	X	X	X	X		X		
Stool collection ⁱ	X			X ⁱ				
Tumor biopsy ^j	X ^k			X ^j		X ^j		
Concomitant medications ^l	X	X	X	X	X	X	X	
Adverse events ^l	X	X	X	X	X	X	X	

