^j Participants will undergo up to 4 tumor biopsies: mandatory baseline biopsy (for treatment assignment based on percent of tumoral CD8 cells), ± 3 days of the 2nd dose of nivolumab and within 3 days of the 4th dose of nivolumab (Day 22 of Cycles 1 and 2, respectively; however, any on treatment biopsy after Day 22 of Cycles 1 and 2 will be accepted, if medically feasible), biopsy may occur prior to dosing. Regardless of dosing, participants should continue to follow assessments as timed. Additionally, an optional tumor biopsy at the time of progression may be obtained.

^k If the results of the baseline screening biopsy are not adequate to obtain information on the percentage of tumoral CD8 cells for treatment assignment, a 2nd baseline biopsy may be obtained, if it is medically feasible and the participant is willing to undergo another tumor biopsy. Additionally, if the results of the on treatment biopsy are not adequate to obtain information on the percentage of tumoral CD8 cells, a 2nd on treatment biopsy may be obtained, if it is medically feasible and the participant is willing to undergo another tumor biopsy.

^l All AEs, SAEs, and all concomitant medications will be collected from the time the participant signs informed consent until 100 days after the last dose of study intervention. Prior to initiation of study intervention, only AEs and SAEs that are related to a protocol mandated intervention, including those that occur

prior to assignment of study procedures (eg, screening invasive procedures, such as biopsies) should be reported. Trial-limiting toxicities can be found in [Section 8.3.7](#).

- ^m Nivolumab will be administered in combination with ipilimumab. Two cohorts will receive combination therapy. Prostate Cohort A will receive nivolumab **1 mg/kg Q3W (4 doses over 2 cycles)** and ipilimumab **3 mg/kg Q6W (2 doses over 2 cycles)**. Participants will then receive nivolumab at **480 mg IV Q4W** until PD or intolerable toxicity (starting at Cycle 3). Prostate Cohort B will receive nivolumab **1 mg/kg Q3W (4 doses over 2 cycles)** and ipilimumab **5 mg/kg Q6W (2 doses over 2 cycles)**. Participants will then receive nivolumab at **480 mg IV Q4W** until PD or intolerable toxicity (starting at Cycle 3).
- ⁿ Beginning at Cycle 3, nivolumab maintenance (nivolumab at 480 mg IV Q4W) will be administered until PD or intolerable toxicity.

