6.1 STUDY INTERVENTION(S) ADMINISTERED

The study interventions to be administered in this study are summarized in [Table 6](#).

Table 6: Study Intervention

Study Intervention Name	Dosage Formulation	Unit Dose Strength(s)	Dosage Level(s)	Route of Administration	Sourcing
Advanced Metastatic Cancer					
Nivolumab	Aqueous solution	10 mg/mL	360 mg (administered with ipilimumab) 480 mg (maintenance)	Intravenous	Bristol-Myers Squibb
Ipilimumab	Aqueous solution	5 mg/mL	1 mg/kg (administered with nivolumab)	Intravenous	Bristol-Myers Squibb
Advanced Prostate Cancer					
Nivolumab	Aqueous solution	10 mg/mL	1 mg/kg (administered with ipilimumab) 480 mg (maintenance)	Intravenous	Bristol-Myers Squibb
Ipilimumab	Aqueous solution	5 mg/mL	3 or 5 mg/kg (administered with nivolumab)	Intravenous	Bristol-Myers Squibb

Participants with $\geq 15\%$ CD8 cells in their tumor biopsy enrolled on the CD8 high arm will be treated with single-agent nivolumab until disease progression. Additionally, participants enrolled on the CD8 high arm in this study could, at disease progression, cross-over to the CD8 low arm; participants with advanced prostate cancer enrolled under Amendment 3+ who cross-over to the CD8 low arm will be placed in Prostate Cohort A.

Nivolumab monotherapy and nivolumab in combination with ipilimumab will be administered as described below.

- *Nivolumab monotherapy (Advanced Metastatic Cancer and Advanced Prostate Cancer):* Nivolumab will be administered at 360 mg as an IV infusion over approximately 30 minutes Q3W \pm 3 days (see [Section 4.3.1](#)). Participants who

continue to show clinical benefit after the first disease assessment will receive nivolumab maintenance 480 mg IV Q4W \pm 3 days until PD or intolerable toxicity (starting at Cycle 5).

- ***Nivolumab in combination with ipilimumab (Advanced Metastatic Cancer):***

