Nivolumab will be administered at 360 mg as an IV infusion over approximately 30 minutes Q3W \pm 3 days (see [Section 4.3.2](#)), followed approximately 30 minutes later by ipilimumab, which will be administered at 1 mg/kg as an IV infusion over approximately 30 minutes ([Momtaz et al, 2015](#)). Ipilimumab will be administered Q3W \pm 3 days for the first 2 doses and then every 6 weeks for the 3rd and 4th doses, followed by nivolumab maintenance 480 mg IV Q4W \pm 3 days until PD or intolerable toxicity (starting at Cycle 7). Each of the subsequent doses will be administered as nivolumab maintenance 480 mg IV Q4W \pm 3 days over approximately 30 minutes.
- ***Nivolumab in combination with ipilimumab (Advanced Prostate Cancer):***
Participants in the < 15% CD8 cells (CD8 low) arm will receive either one of the following combinations of nivolumab and ipilimumab:
 - **Prostate Cohort A:** Nivolumab will be administered at 1 mg/kg as an IV infusion over approximately 30 minutes Q3W (see [Section 4.3.2](#)), followed approximately 30 minutes later by ipilimumab, which will be administered at 3 mg/kg as an IV infusion over approximately 30 minutes ([Momtaz et al, 2015](#)) Q6W for two 6 week cycles. After completion of 2 cycles, nivolumab maintenance 480 mg IV Q4W \pm 3 days will be administered until PD or intolerable toxicity.
 - **Prostate Cohort B:** Nivolumab will be administered at 1 mg/kg as an IV infusion over approximately 30 minutes Q3W (see [Section 4.3.2](#)), followed approximately 30 minutes later by ipilimumab, which will be administered at 5 mg/kg as an IV infusion over approximately 30 minutes ([Momtaz et al, 2015](#)) Q6W for two 6 week cycles. After completion of 2 cycles, nivolumab maintenance 480 mg IV Q4W \pm 3 days will be administered until PD or intolerable toxicity.

For all study interventions, either a peripheral IV or central port or line is acceptable for infusion. Administration of study intervention will be performed in a monitored setting in which there is immediate access to trained personnel and adequate equipment and medicine to manage potentially serious reactions.

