8 STUDY ASSESSMENTS AND PROCEDURES

Please see [Section 1.3](#) for the SOAs to be performed during the study. All activities must be performed and documented for each participant in the order of SOAs. Participants will be closely monitored for safety and tolerability throughout the study. Participants should be assessed for toxicity prior to each dose; dosing will occur only if the clinical assessment and local laboratory test values are acceptable as deemed by the PI.

If the timing of a protocol-mandated study visit coincides with a holiday, weekend, or other administrative disruption that precludes the visit, the visit should be scheduled on the nearest following feasible date. The time between doses must not be less than minus 3 days from the normal schedule of the last dose received (doses must not be administered < 25 days for a Q4W schedule or < 18 days apart for a Q3W).

Collection of any non-safety-related data or participant samples may be terminated by the Sponsor at any time if further collection of such data or samples is also not related to the study's primary or secondary objective. The decision to discontinue any data collection will be communicated to the sites and Institutional Review Board (IRB)/Independent Ethics Committee (IEC) by means of a memorandum and will not require a protocol amendment.

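### The footnote on both dosing rows of the combination-arm schedule (Protocol Table 2, footnote n) gives the monotherapy regimen: maintenance from Cycle 5 instead of Cycle 7, and no ipilimumab

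*Protocol*

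**What the plan says.** Table 2 in Protocol Section 1.3 is titled as the combination-arm schedule. Footnote n is attached to its nivolumab row and to its ipilimumab row ("Ipilimumab administration ⁿ").

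- **Footnote n:** "Nivolumab monotherapy will be administered at 360 mg IV Q3W for 4 cycles". Participants with continuing clinical benefit after the first disease assessment then "will receive nivolumab at 480 mg IV Q4W until PD or intolerable toxicity (starting at Cycle 5"). Ipilimumab is not mentioned.
- **Footnote o, directly below it:** "Beginning at Cycle 7, nivolumab maintenance (nivolumab at 480 mg IV Q4W) will be administered until PD or intolerable toxicity".
- **Grid:** the footnote o marker sits on the Cycle 7 nivolumab dose. Ipilimumab is marked at Cycles 1, 2, 4 and 6.
- **Footnote k:** the biopsy after the fourth ipilimumab dose falls in Cycle 6.
- **Section 6.1, combination regimen for advanced metastatic cancer:** maintenance runs "until PD or intolerable toxicity (starting at Cycle 7").
- **Table 6:** the nivolumab dose levels are "360 mg (administered with ipilimumab") and 480 mg for maintenance.
- **Section 8, minimum spacing:** "doses must not be administered < 25 days for a Q4W schedule or < 18 days apart for a Q3W".

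**The concern.** The footnote that a pharmacist or coordinator reaches from the dosing rows describes a different arm. It brings the dose change forward by two cycles, into a period when ipilimumab is still being given, and it omits the ipilimumab dose that its own row should carry.

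Three uses of the schedule make this worth correcting even though the intent can be recovered:

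- **Overdose reporting.** Section 8.4 counts any dose above the protocol-specified one as an overdose, to be reported as an SAE and recorded as a deviation. Against Section 6.1, 480 mg at Cycle 5 or 6 qualifies; against footnote n, it is the specified dose.
- **Exposure summaries.** SAP Section 5.6.1 summarises the number of doses, cumulative dose and skipped doses by arm. These are easiest to interpret against a single planned regimen.
- **Crossover.** Participants who progress on monotherapy in the advanced metastatic portion can cross over to this same combination regimen (Figure 1, footnote c), so the reach is wider than the participants first assigned to the arm.

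**Working it through.** The plan states no figure to reproduce. The check compares texts and counts cycle times.

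**1. Where the footnote text comes from**

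| Table | Arm | Dosing footnote describes |
|---|---|---|
| 1, footnote n | Metastatic, monotherapy | Monotherapy, 480 mg from Cycle 5 |
| 2, footnote n | Metastatic, combination | The same text as Table 1 footnote n |
| 3, footnote m | Prostate, monotherapy | The same text again |
| 4, footnote m | Prostate, combination | Its own regimen: "Nivolumab will be administered in combination with ipilimumab. Two cohorts will receive combination therapy" |

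Table 2 is the only combination table whose dosing footnote is monotherapy text. A copying slip is an inference, but a strong one. The contradiction does not depend on how it arose.

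**2. Nominal cycle starts in weeks**

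Inputs: Q3W and Q4W spacing, with maintenance from Cycle 7 (Section 6.1) or Cycle 5 (footnote n).

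| | C1 | C2 | C3 | C4 | C5 | C6 | C7 |
|---|---|---|---|---|---|---|---|
| Section 6.1 | 0 | 3 | 6 | 9 | 12 | 15 | 18 |
| Footnote n | 0 | 3 | 6 | 9 | 12 | 16 | 20 |

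**3. Which version fits the ipilimumab schedule**

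Under Section 6.1, ipilimumab at Cycles 1, 2, 4 and 6 falls at weeks 0, 3, 9 and 15. The gaps are 3, 6 and 6 weeks, which match the stated plan of Q3W for the first two doses and every 6 weeks for the third and fourth. Under footnote n spacing, a fourth dose tied to Cycle 6 falls at week 16, a gap of 16 − 9 = 7 weeks. If the 6-week interval were kept instead, the dose would stay at week 15 but would no longer coincide with Cycle 6.

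**4. Can both texts be met?**

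Cycle 5 to Cycle 6 interval:

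- Section 6.1: 21 ± 3 = 18–24 days.
- Footnote n: 28 ± 3 = 25–31 days, with Section 8 ruling out anything under 25 days for Q4W.

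The windows do not overlap. The doses differ as well: 360 mg against 480 mg at Cycles 5 and 6.

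**5. Nivolumab exposure**

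- Average rate: 360/3 = 120 mg/week and 480/4 = 120 mg/week, so they are equal.
- Cumulative dose depends on when it is counted:

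| Just before week | Section 6.1 | Footnote n |
|---|---|---|
| 15 | 5 × 360 = 1800 mg | 4 × 360 + 480 = 1920 mg |
| 16 | 6 × 360 = 2160 mg | 1920 mg |
| 18 | 2160 mg | 4 × 360 + 2 × 480 = 2400 mg |
| 20 | 2160 + 480 = 2640 mg | 2400 mg |

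The sign of the difference alternates. No cumulative excess should be claimed; the difference lies in dose size and timing at Cycles 5 and 6.

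**The case against.** The best defence is that nobody would be misled. The footnote opens by naming monotherapy, in a table titled for the combination and containing an ipilimumab row, so it reads as a stray note about the other arm. The synopsis, Figure 2, Section 4.3.2, Section 6.1 and the SAP (Section 3 and its appended synopsis) all give the combination doses. Taken literally, footnote n means no ipilimumab at all, so the timing scenarios above combine its nivolumab with the grid's ipilimumab, a regimen that no text describes. The grid is also not fully independent evidence on when maintenance starts, because it speaks to that only through the footnote o marker. Nothing in the documents suggests that anyone was misdosed.

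Most of this stands, and it limits the importance of the point. It does not make the footnote right: it is the reference attached to the dosing rows, and Section 6.1 contradicts it independently of the grid.

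A second defence is the early-stopping allowance. Under the synopsis, participants who stop ipilimumab because of toxicity may begin maintenance after about 12 weeks of nivolumab, close to Cycle 5 (Section 6.6.1 has a similar allowance without the timing). Footnote n does not state that exception. Its condition is clinical benefit at the first disease assessment, not toxicity. The allowance does bear on how the replacement is worded.

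**Conclusion.** The concern holds: Table 2 footnote n is wrong for the arm it serves. A site that applied its nivolumab instruction would give 480 mg instead of 360 mg at Cycles 5 and 6, start Q4W spacing at week 12 instead of week 18, and do so before the fourth ipilimumab dose.

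This is a minor documentation error. The intended regimen can be recovered without doubt. Biopsy timing is largely protected because footnote k accepts later on-treatment biopsies, and scan timing by the ± 7-day window. No endpoint, sample size, stopping rule or analysis changes. The timings assume nominal dosing with no delays, and the week-16 figure further assumes that ipilimumab stays tied to Cycle 6.

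**What to change.** Replace Table 2 footnote n with the Section 6.1 combination regimen:

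- nivolumab 360 mg IV Q3W at Cycles 1–6;
- ipilimumab 1 mg/kg IV at Cycles 1, 2, 4 and 6;
- nivolumab 480 mg IV Q4W from Cycle 7 (see footnote o).

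Remove the Cycle 5 start from this table. Add a cross-reference to Section 6.6.1 and the synopsis for participants who stop ipilimumab early because of toxicity, so that the new footnote does not appear to withdraw that option. The cost is one footnote in the next amendment or a clarification letter.
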